1. INTRODUCTION

This statistical analysis plan (SAP) is based on Molecular Templates' Protocol # MT-3724_NHL_003, titled "A Phase 2a Open-label Study to Investigate Safety and Tolerability (including the MTD), Efficacy, Pharmacokinetics, Pharmacodynamics and Immunogenicity of MT-3724 in Combination with Lenalidomide in Subjects with Relapsed or Refractory B-cell Non-Hodgkin Lymphoma". See the study Protocol for details on study rationale, conduct and endpoints.

The purpose of this SAP is to provide details of the statistical analyses specified in the study protocol. The SAP summarizes key aspects of the study to provide context for statistical methods and presents details of the planned statistical methods following the completion of the trial.

This study will be conducted in compliance with the study protocol and ICH guideline E9 ([Statistical Principles for Clinical Trials 1998](#)).

2. OBJECTIVES AND ENDPOINTS

2.1 Objectives

2.1.1 Primary Objective

The primary objective of the study is to determine the safety and tolerability (including the MTD) of MT-3724 in combination with lenalidomide in subjects with relapsed or refractory B-Cell NHL.

2.1.2 Secondary Objectives

The secondary objectives of the study are to:

- Characterize the PK of MT-3724 in combination with lenalidomide in subjects with relapsed or refractory B-cell NHL
- Assess the PD of MT-3724 in combination with lenalidomide in subjects with relapsed or refractory B-cell NHL
- Assess the immunogenicity of MT-3724 in combination with lenalidomide in subjects with relapsed or refractory B-cell NHL
- Assess the tumor response to MT-3724 in combination with lenalidomide in subjects with relapsed or refractory B-cell NHL

3. INVESTIGATIONAL PLAN

3.1 Study Design

This is a multi-center, open-label, multiple-dose Phase 2a, dose-escalation study of MT-3724 in combination with LEN in subjects with relapsed or refractory B-Cell NHL. Eligible subjects will be identified and treated through competitive enrollment at multiple study centers in North America and Europe.

The study will be conducted in two sequential parts (Part 1 and Part 2); in both parts of the study, the subject's participation in the study will comprise 2 periods: screening and treatment.

Part 1 will include MT-3724 dose escalation according to the modified 3+3 design to identify the MTD of MT-3724 in combination with fixed standard doses of LEN. If permitted by the safety results, the MT-3724 dose escalation is planned to proceed in three sequential dose cohorts (Cohorts 1-3).

The purpose of Part 2 is to confirm the safety and tolerability of the MTD of MT-3724 from Part 1 in the MTD Expansion Cohort, where MT-3724 will be given at the MTD in combination with LEN. In addition, the PK, PD, immunogenicity and tumor response at the MTD of MT-3724 in combination with LEN will be more thoroughly evaluated in Part 2.

See the study protocol for full study design details.

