Cohort management and dose escalation decisions (including the MTD) will be based on the incidence of TEAEs that fulfill the criteria for a DLT, as follows:

- The first dose escalation decision in the current MT-3724 dose cohort will be made after at least 3 subjects complete cycle 1 or experience a DLT. Up to 4 subjects may be initially treated in each MT-3724 dose cohort; this aims to ensure that at least 3 evaluable subjects are available for the first dose escalation decision.
- If none of the first 3 or 4 subjects in the current MT-3724 dose cohort experience a DLT, then dose escalation may proceed to the next planned MT-3724 dose level.
- If 1 of the initial 3 or 4 subjects in the current MT-3724 dose cohort experiences a DLT, then this cohort will be expanded to 6 subjects. Subjects for the expanded current cohort may be enrolled simultaneously through competitive enrollment.

- d. If no more than 1 of 6 subjects in the expanded current MT-3724 dose cohort experiences a DLT, then dose escalation may proceed to the next planned MT-3724 dose level.
- e. If a DLT occurs in ≥ 2 of initial 3 or 4 subjects in the current MT-3724 dose cohort, or in ≥ 2 of 6 subjects in the expanded current cohort, one of the following 2 steps may be undertaken at the sponsor's discretion after consultation with the investigator(s):
 - If not previously done, up to 6 subjects may be treated at the planned MT-3724 dose level immediately below the non-tolerable dose.
 - Alternatively, up to 4 subjects may be initially treated at the 'interim' MT-3724 dose level and schedule between the non-tolerable dose level and the planned MT-3724 dose level immediately below the non-tolerable dose. The MT-3724 doses proposed for the 'interim' cohorts are listed in [Table 5](#); however the actual MT-3724 doses and schedule for 'interim' cohorts will be recommended by the sponsor after consultation with all investigators.
- f. If at least 4 subjects in the cohort have no DLTs, dose re-escalation can be attempted in up to 6 subjects at the original target dose of the previous cohort under the new schedule after consultation with the investigators and medical monitor.
- g. The same principles as listed above will apply to the cohort management and dose decisions in the 'interim' MT-3724 dose cohorts.

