3.6.3 MTD definition

The highest MT-3724 dose that can be given in combination with LEN so that no more than 1 of 6 subjects experiences a DLT will be declared as the MTD for MT-3724 in Part 1 of this study. At least 6 subjects must be treated at the MTD dose level of MT-3724 in combination with LEN and complete cycle 1 or experience a DLT.

The MTD decision will be made by the sponsor after consultation with all investigator.

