5.1.3 MT-3724 dosing schedule

MT-3724 will be administered as an IV infusion over 1 hour (window of 54-75 minutes).

Cohort 1-3

For subjects enrolled in Cohorts 1-3, in cycles 1 and 2, MT-3724 infusion should be administered on Day 1, 3, 5, 8, 10 and 12 (± 1) of each 28-day cycle.

Cohorts ≥ 4

In subsequent cohorts in cycles 1 and 2, MT-3724 infusion should be administered on Days 1, 5, 8 and 12 (± 1) of each 28-day cycle. Different dosing days up to D21 may be selected at investigator's discretion after consultation with the medical monitor.

All Cohorts

Starting with cycle 3, MT-3724 will be administered weekly (Day 1, 8, 15 and 22) of each 28-day cycle. Different dosing days within ± 2 days from Day 1, 8, 15 and 22 may be selected at investigator's discretion.

Time windows for days of MT-3724 dosing

Cycles 1-2

Any of the scheduled MT-3724 doses may be administered on different dosing days at investigator's discretion up to D21.

MT-3724 doses must be administered at least 48 hours apart.

Cycles 3 and beyond

Any of the scheduled weekly MT-3724 doses may be administered within ± 2 days at investigator's discretion.

For all cycles

No more than 14 days should elapse between cycles. If more than 14 days elapse, the investigator must consult with the medical monitor before initiating the next cycle of treatment.

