7.2 General statistical considerations

Statistical analysis will be performed using the Statistical Analysis System®; the version used will be specified in the statistical analysis plan (SAP).

All data will be listed, and descriptive summary tables will be provided by treatment group/cohort irrespective of the study part. In addition, appropriate variables will be summarized in a separate treatment group comprising the subjects treated at the MTD of MT-3724 in Part 1 (dose escalation) and in Part 2 (expansion). These variables will be specified in the SAP.

Quantitative data will be described by the following summary statistics: arithmetic mean, standard deviation, median, minimum, and maximum. Where appropriate, descriptive summary statistics will be tabulated for the absolute values and changes from baseline. Graphical illustrations will be provided where appropriate. Qualitative data will be presented in the frequency tables.

The assessment obtained at the most recent time before the start of MT-3724 treatment will be the baseline for all post-baseline assessments. The value obtained before MT-3724 Dose 1 on C1D1 (if available) will serve as the baseline; if not available, then the value obtained earlier at screening will serve as the baseline.

Further details about the statistical analyses will be provided in the SAP. Any changes in the statistical methods described herein compared to the final SAP will be documented in the integrated clinical study report.

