3.2 Treatment

MT-3724 will be administered as intravenous (IV) infusion over 1 hour.

In Part 1 (MT-3724 dose escalation), the starting MT-3724 doses in each of the planned cohorts will be:

1. 10 µg/kg/dose in Cohort 1
2. 25 µg/kg/dose in Cohort 2
3. 50 µg/kg/dose in Cohort 3

Additional interim dose cohorts may be evaluated only if warranted by the safety results in the previous planned cohorts. The maximum dose of MT-3724 that will be given in this study is 50 µg/kg/dose.

In Part 2 (Expansion Cohort), the starting MT-3724 dose will be the MTD of MT-3724 from Part 1.

The administered dose of MT-3724 for subjects will be capped at 6000 µg per infusion. Intra-subject escalation of MT-3724 dose is not permitted in this study. The guidance for treatment modification (dose interruption / delay, dose reduction or treatment discontinuation) is outlined in the study protocol.

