3.2.1 Dosing Schedule

MT-3724 Dosing Schedule

Cycles 1-2

In Cycle 1 and Cycle 2, MT-3724 should be administered as 1-hour IV infusion on Day 1, 3, 5, 8, 10 and 12 of each 28-day cycle.

Any of the scheduled MT-3724 doses may be administered on different dosing days at investigator's discretion up to D21. However, no more than two MT-3724 doses can be administered on consecutive days.

If MT-3724 is administered on consecutive days, then at least 20 hours (approximately five half-lives of MT-3724 in plasma) must elapse between the start of the 2 infusions.

The "catch up" on missed MT-3724 doses in the current cycle is allowed at the investigator's discretion up to D21. MT-3724 should not be administered between D21-D28 in C1-C2.

MT-3724 may be continued in C3-C4 (with or without LEN) if supported by the investigator's assessment of the benefit-risk ratio.

Cycles 3-4 (if applicable or beyond)

If treatment is continued, then dosing in C3-C4, MT-3724 should be administered as 1-hour IV infusion weekly (Day 1, 8, 15 and 22 of each 28-day cycle). Any of the scheduled weekly MT-3724 doses may be administered within ± 2 days at investigator's discretion. MT-3724 should not be administered between D24-D28 in C3-C4.

Lenalidomide Dosing Schedule

In both parts of the current study, subjects will self-administer LEN qd PO with or without food, around the same time each day, on the first 21 consecutive days (Day 1-Day 21) of each 28-day cycle. LEN cannot be administered between D22-D28 in any cycle.

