8.1 Extent of Exposure

The total number of doses received, the expected total dose, the actual dose administered, and outcome of infusion will be summarized and presented. Information in the listing will include total dose of MT-3724 administered, start and stop times, outcome of infusion, and duration of interruption (if applicable).

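### SAP 3.1 to 3.2.1 give three cohorts on one six-infusion schedule where the current protocol has five planned cohorts on two schedules; the MTD and the combined MTD group are defined by dose without schedule

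*SAP*

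**What the plan says.** **Design in the SAP.** SAP 3.1 states that "the MT-3724 dose escalation is planned to proceed in three sequential dose cohorts (Cohorts 1-3". SAP 3.2 then says "the starting MT-3724 doses in each of the planned cohorts will be" 10, 25 and 50 µg/kg for Cohorts 1, 2 and 3. SAP 3.2.1 gives one early schedule: "In Cycle 1 and Cycle 2, MT-3724 should be administered as 1-hour IV infusion on Day 1, 3, 5, 8, 10 and 12". From cycle 3, dosing is weekly.

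**Design in the protocol.** Table 5 (section 3.6) has five planned cohorts: 10, 25 and 20 µg/kg three times weekly (TIW) in Cohorts 1 to 3, then 25 and 50 µg/kg twice weekly (BIW) in Cohorts 4 and 5. Section 5.1.3 keeps the six-infusion schedule for Cohorts 1 to 3 and continues: "In subsequent cohorts in cycles 1 and 2, MT-3724 infusion should be administered on Days 1, 5, 8 and 12". From cycle 3, all cohorts are dosed weekly.

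**Exposure.** SAP 8.1 says: "The total number of doses received, the expected total dose, the actual dose administered, and outcome of infusion will be summarized and presented". No formula is given.

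**MTD and combined group.** Protocol 3.6.3 defines the MTD as "The highest MT-3724 dose that can be given in combination with LEN so that no more than 1 of 6 subjects experiences a DLT". Protocol 7.2 plans "a separate treatment group comprising the subjects treated at the MTD of MT-3724" across Parts 1 and 2, and SAP 5 combines cohorts at the recommended phase 2 dose (RP2D). None of the three names a schedule. Under protocol 3.6, rule (f), "dose re-escalation can be attempted in up to 6 subjects at the original target dose of the previous cohort under the new schedule".

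**The concern.** The SAP's Cohort 3 dose differs from the protocol's, and Cohorts 4 and 5 and all BIW dosing are missing from it. Anyone programming exposure from the SAP alone would find only a six-infusion schedule for cycles 1-2. Applied to a BIW cohort, that schedule would make fully dosed subjects look under-dosed, in a summary that supports the primary safety and tolerability objective.

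The second matter is the label on the combined group. It should describe the regimen carried into Part 2. Since 25 µg/kg is planned on both schedules, a group selected on dose alone could take in subjects treated on a different regimen.

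**Working it through.** **1. The protocol's own figures.** Protocol 3.6.1 requires 4 of 6 doses (67%) or 3 of 4 doses (75%) in cycle 1 for a subject without a DLT to be evaluable. 4/6 = 66.7% and 3/4 = 75.0%, so both reproduce, and they confirm six and four planned infusions on the two schedules. SAP 5.4 has only a 4-of-6 rule, labelled 83%. That label does not reproduce (4/6 = 66.7%; 5/6 = 83.3%), and there is no four-dose version.

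**2. Cohorts side by side.** Doses are in µg/kg. Infusions over cycles 1-2 are 6 + 6 = 12 on the SAP and TIW schedules, and 4 + 4 = 8 on BIW. Cumulative dose = dose per infusion × infusions.

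| Cohort | SAP dose | Protocol dose and schedule | Protocol dose × 12 (SAP schedule) | Protocol dose × protocol infusions |
|---|---|---|---|---|
| 1 | 10 | 10 TIW | 120 | 120 |
| 2 | 25 | 25 TIW | 300 | 300 |
| 3 | 50 | 20 TIW | 240 | 240 |
| 4 | not listed | 25 BIW | 300 | 200 |
| 5 | not listed | 50 BIW | 600 | 400 |

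For the BIW cohorts the ratio is 12/8 = 1.5.

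**3. Apparent share of expected dose, if the quantity is cumulative and uses the SAP schedule.** Through cycle n (n ≥ 2) the SAP schedule gives 12 + 4(n − 2) infusions and BIW gives 8 + 4(n − 2). A BIW subject who receives every planned infusion then shows:

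- through cycle 2: 8/12 = 67%
- through cycle 4: 16/20 = 80%
- through cycle 6: 24/28 = 86%

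Body weight and the 6000 µg cap per infusion act on each infusion alike, so they do not change these ratios.

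**4. If the quantity is per infusion.** The number of infusions drops out and the share is 100%. What remains is the Cohort 3 dose, 50 against 20 µg/kg (50/20 = 2.5-fold), and only if someone used the SAP's figure instead of the assigned dose.

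**5. Combined group.** Among the planned cohorts, 25 µg/kg is the only dose on both schedules (Cohort 2 TIW, Cohort 4 BIW). In cycles 1-2 these are 25 × 6 = 150 and 25 × 4 = 100 µg/kg per cycle. The cohort sizes are not given, so I assume 3 to 6 subjects in Cohort 2, 6 in Cohort 4 and 40 in Part 2. If the MTD were 25 BIW and the group were chosen on dose alone:

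- 3 + 6 + 40 = 49 subjects, of whom 3/49 = 6% had TIW dosing
- 6 + 6 + 40 = 52 subjects, of whom 6/52 = 12% had TIW dosing

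If the MTD is 20 TIW or 50 BIW, no other planned cohort shares the dose and the question does not arise.

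**The case against.** **On exposure.** SAP section 1 presents the study description as context for the methods, and SAP 3.1 sends the reader to the protocol for the full design. The SAP's precedence clause (section 4) covers statistical methods, not design background. Protocol 5.7 already judges compliance by comparing actual with planned dosing. A programmer would have to take Cohort 4 or 5 from Table 5 and ignore the BIW label in the same cell. Expected total dose may also be per infusion: protocol 1.6 and 5.1.2 use total dose in that sense, and SAP 8.1 sets it beside infusion outcome, start and stop times and interruptions.

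All of this stands as a limit on the consequence. A reader might infer that the SAP will misstate BIW exposure. The documents do not show that, because SAP 8.1 has no formula and does not point to SAP 3.2.1. The objection leaves the textual conflict and the missing formula in place.

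**On the MTD.** Appendix 9 reports DLTs in two Cohort 2 subjects, so under rule (e) 25 TIW is not tolerable and cannot itself be the MTD. Declaring 25 BIW the MTD would already take schedule into account. Table 5 labels every level TIW or BIW, and rules (e) and (f) mention schedule. This makes the dose-and-schedule reading the more natural one. It does not put schedule into the three definitions.

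**On DLT reporting.** A reader might also infer that the DLT summary by dose level (SAP 8.2.7) would merge 25 TIW with 25 BIW. The documents point the other way: Table 5 lists them as separate levels, protocol 7.8 presents safety by dose and regimen, protocol 7.8.1 lists DLTs by cohort, and SAP 5 reports escalation cohorts separately.

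**Conclusion.** The mismatch between SAP 3.1 to 3.2.1 and the current protocol is plain: three cohorts against five, 50 against 20 µg/kg in Cohort 3, and no BIW schedule. That the SAP follows a superseded design is an inference from this mismatch, since its date and base protocol version cannot be seen.

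The consequences are conditional. The 67%, 80% and 86% figures hold only if expected total dose is cumulative and is programmed from the SAP schedule. The 6-12% share of TIW subjects holds only if the MTD is 25 BIW, the combined group is read literally on dose, and the cohort sizes are as assumed. A reader might infer that dose escalation is compromised. It is not, because decisions are made cohort by cohort under protocol 3.6 and do not use these SAP sections. Nor does any test or sample size change, as the study is descriptive. Severity is minor to moderate.

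**What to change.** - Update SAP 3.1, 3.2 and 3.2.1 to the current protocol: five planned cohorts, the correct Cohort 3 dose, and both cycle 1-2 schedules.
- In SAP 8.1, say whether expected total dose is cumulative or per infusion, and compute it from each subject's own cohort dose and schedule.
- In protocol 3.6.3, state the MTD as a dose-schedule pair.
- In protocol 7.2 and SAP 5, limit the combined MTD/RP2D group to subjects on that same dose and schedule.

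The cost is a rewrite of three short SAP sections and a few phrases elsewhere in the two documents. No extra patients or assessments are needed.

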3.2 Treatment

MT-3724 will be administered as intravenous (IV) infusion over 1 hour.

In Part 1 (MT-3724 dose escalation), the starting MT-3724 doses in each of the planned cohorts will be:

1. 10 µg/kg/dose in Cohort 1
2. 25 µg/kg/dose in Cohort 2
3. 50 µg/kg/dose in Cohort 3

Additional interim dose cohorts may be evaluated only if warranted by the safety results in the previous planned cohorts. The maximum dose of MT-3724 that will be given in this study is 50 µg/kg/dose.

In Part 2 (Expansion Cohort), the starting MT-3724 dose will be the MTD of MT-3724 from Part 1.

The administered dose of MT-3724 for subjects will be capped at 6000 µg per infusion. Intra-subject escalation of MT-3724 dose is not permitted in this study. The guidance for treatment modification (dose interruption / delay, dose reduction or treatment discontinuation) is outlined in the study protocol.

3.2.1 Dosing Schedule

MT-3724 Dosing Schedule

Cycles 1-2

In Cycle 1 and Cycle 2, MT-3724 should be administered as 1-hour IV infusion on Day 1, 3, 5, 8, 10 and 12 of each 28-day cycle.

Any of the scheduled MT-3724 doses may be administered on different dosing days at investigator's discretion up to D21. However, no more than two MT-3724 doses can be administered on consecutive days.

If MT-3724 is administered on consecutive days, then at least 20 hours (approximately five half-lives of MT-3724 in plasma) must elapse between the start of the 2 infusions.

The "catch up" on missed MT-3724 doses in the current cycle is allowed at the investigator's discretion up to D21. MT-3724 should not be administered between D21-D28 in C1-C2.

MT-3724 may be continued in C3-C4 (with or without LEN) if supported by the investigator's assessment of the benefit-risk ratio.

Cycles 3-4 (if applicable or beyond)

If treatment is continued, then dosing in C3-C4, MT-3724 should be administered as 1-hour IV infusion weekly (Day 1, 8, 15 and 22 of each 28-day cycle). Any of the scheduled weekly MT-3724 doses may be administered within ± 2 days at investigator's discretion. MT-3724 should not be administered between D24-D28 in C3-C4.

Lenalidomide Dosing Schedule

In both parts of the current study, subjects will self-administer LEN qd PO with or without food, around the same time each day, on the first 21 consecutive days (Day 1-Day 21) of each 28-day cycle. LEN cannot be administered between D22-D28 in any cycle.

4. CHANGES TO PLANNED ANALYSIS

The statistical methods described in this SAP take precedence over the protocol. Additional exploratory efficacy endpoints have been added.

- [REDACTED]
- [REDACTED]

5. GENERAL CONSIDERATIONS FOR DATA ANALYSIS

Quantitative data will be described by the following summary statistics: arithmetic mean, standard deviation, median, minimum, and maximum. Where appropriate, descriptive summary statistics will be tabulated for the absolute values and changes from baseline. Graphical illustrations will be provided where appropriate. Qualitative data will be presented in the frequency tables.

Analyses will be performed using SAS for Windows statistical software, version 9.2 or higher (SAS, Cary, NC), except where other software may be deemed more appropriate.

CTI Clinical Trial and Consulting Services (Cincinnati, OH) will perform all efficacy and safety statistical analyses.

Subject data will be listed, sorted by cohort and subject number. Dose escalation cohorts and MTD expansion cohort will be reported separately and combined at the recommended phase 2 dose.

5.1 Data Quality Assurance

Molecular Templates, or its designated representative, will conduct a pre-study visit for each study site to verify the qualifications of the investigator, inspect study site facilities, become familiarized with site staff assigned to the study, and inform the investigator of responsibilities and procedures for ensuring correct study documentation.

A study coordinator at the investigative site will enter subject data into a remote data capture

database (RDC) by completing electronic case report forms (eCRFs). All information recorded in the eCRFs for this study must be consistent with the investigator's source documentation for the study participants. The investigative site will make available source documents to CTI personnel monitoring the study. The study monitor will verify consent of all subjects to participate in the study and will perform 100% source document verification of the eCRF data.

A CTI Clinical Data Associate (CDA) will review the data for discrepancies via programmed electronic consistency checks, data listings, or manually. Any discrepancies discovered via the data review process will be issued as queries in the RDC system to the investigative site for resolution. Once all the source verification is complete, all queries are resolved, and the database has been updated appropriately, the database will be locked and made available to CTI Biostatistics for analysis.

Data may be pulled by CTI Biostatistics for interim analysis at a time when source verification and query resolution is ongoing. No interim statistical analysis is planned during either part of this study. An interim statistical analysis may be performed only pursuant to a health authority request.

All SAS programs used to create analysis datasets and output will be validated by ensuring that the “.log” files are void of all errors, warnings and notes indicative of problems. Additionally, each program will be checked to ensure that it performs according to the program specification. All programs are developed and validated by separate members of the CTI Biostatistics Department.

At the time of analysis, a quality control (QC) review of database values listed in SAS output will be compared to the database. The sample size of fields to undergo QC review will be determined by utilizing American National Standards Institute (ANSI) sampling procedures¹. Sampling procedures are conducted using “normal” inspection criteria (Inspection Level II, Single, and Normal) and an Acceptable Quality Level (AQL) of 0.010%. The following shows the sampling criteria:

Single Normal sampling procedure for Acceptable Quality Level (AQL) 0.010%

Number of Fields	Sample Size	Accept/Reject Criteria
2-8	2	0/1
9-15	3	0/1
16-25	5	0/1
26-50	8	0/1
51-90	13	0/1
91-150	20	0/1
151-280	32	0/1
281-500	50	0/1
501-1,200	80	0/1
1,201-3,200	125	0/1
3,201-10,000	200	0/1
10,001-35,000	315	0/1
35,001-150,000	500	0/1
150,001-500,000	800	0/1

Number of Fields	Sample Size	Accept/Reject Criteria
500,001-up	1,250	0/1

